8.3.9 Serious Adverse Events

A serious adverse event (SAE) is an adverse event occurring at any dose that meets any of the following conditions, regardless of causality:

- Leading to death.
- Life-threatening. Life-threatening refers to an event in which the participant was immediately at risk of death at the time of the event, i.e., excluding an event that hypothetically might have caused death if the event was more severe.
- Requires participant hospitalization or prolongation of hospitalization. A planned hospitalization and/or surgery prior to enrollment of a participant in the study will not be considered an adverse event provided there is no unexpected worsening during the study (e.g., surgery performed earlier than scheduled). Hospitalization for sociality and/or convenience without an untoward medical occurrence is not an adverse event.
 - Resulting in permanent or severe disability/incapacity.
 - Congenital anomaly/birth defect.

• Important medical event. Important medical events are those that may not result in death or be life-threatening or require hospitalization, but may jeopardize the participant or may require medical or surgical intervention to prevent the occurrence of any of the outcomes listed in the definition of an SAE, based on appropriate medical judgment, which are also considered SAEs. Such medical events include allergic bronchospasm requiring intensive treatment in the emergency room or at home, blood cachexia or convulsions that do not require hospitalization, or development of drug dependence or drug abuse.

8.3.10 Suspected unexpected serious adverse reaction

Suspected unexpected serious adverse reaction (SUSAR) refers to a suspected and unexpected serious adverse reaction in which the nature and severity of the clinical manifestation exceeds the available information such as the Investigator's Brochure of the investigational Product, the package insert of a marketed drug, or a summary of product characteristics.

8.3.11 Criteria for Severity of Adverse Events

The investigator will assess the severity of AEs according to the toxicity grades described in the Common Adverse Event Evaluation Criteria NCI-CT CA E 5.0. For AEs not listed in CT CA E 5.0, the following standard grades may be used:

- Grade 1: mild; asymptomatic or mild; clinical or diagnostic findings only; no treatment required.
- Grade 2: moderate; requires small, local, or noninvasive treatment; age-appropriate instrumental activities of daily living (ADL) limitation *.
- Grade 3: serious or medically significant but not immediately life-threatening; resulting in hospitalization or prolongation of hospitalization; disabling; self-Rational ADL Limited * *.
 - Grade 4: life-threatening; urgent treatment is required.
 - Grade 5: deaths related to AEs.
- * Instrumental ADLs refer to cooking, shopping for clothing, using the telephone, managing money, etc.
- * * Self-care ADL refers to bathing, dressing and undressing, eating, washing, taking medications, etc., and not bedridden.

8.3.12 Criteria for Relationship between Adverse Events and Study Drug

The investigator is obligated to make a medical judgment as to the causal relationship between each AE/SAE and the study intervention.

Investigators should consider and investigate other possible etiologies, temporal associations, and use clinical judgment to determine causality. The investigator will determine the relationship to study drug using the following criteria:

Definitely related:	Events or laboratory abnormalities with a reasonable temporal relationship to drug intake; cannot be explained by disease or other drugs; reasonable response after discontinuation (pharmacology, pathology); events identified from a pharmacological or phenomenological perspective (i.e., objective and specific medical conditions or recognized pharmacological phenomena); rechallenge results (if necessary) passed.
Probably related:	Events or laboratory abnormalities with a reasonable temporal relationship to drug intake; not likely attributable to disease or other drugs; reasonable clinical response after discontinuation; rechallenge testing is not required.

Possibly related:	Events or laboratory abnormalities with a reasonable temporal relationship to drug intake; it can also be explained by disease or other drugs; discontinuation information may be missing or equivocal.		
Unlikely related:	Events or laboratory abnormalities that are unlikely (but not impossible) temporally related to drug intake; the disease or other medication may provide a reasonable explanation.		
Not related:	The adverse event was not related to study drug. There is no or little likelihood that the study drug causes an adverse event; other conditions, including intercurrent illness, progression or presentation of the condition condition, or response to concomitant medications, provided a good explanation for the event.		

For safety reporting purposes, in general, all adverse events classified as "definitely related", "probably related" or "possibly related" will be considered treatment related, and adverse events "unlikely related" and "unrelated" will be considered as treatment-unrelated unless specifically specified by the local drug regulatory authority.

The investigator must make a causality determination for each adverse event before reporting to the sponsor, even if the investigator has limited information in the initial report.

The investigator may change the causality determination based on the information obtained at follow-up and update the causality determination in the follow-up report.

8.3.13 Safety Reporting Period

The reporting period for adverse events in this study begins with the signing of informed consent by the participant (prior to any study-related procedures and/or receipt of study drug) until the last Safety Follow-up Visit (7 days after the last dose of the investigational product in Parts I and III; 14 days after the last dose of the investigational product in Part II). Any serious adverse event occurring after the reporting period must also be reported immediately if a causal relationship to the study drug is suspected.

If a participant fails due to laboratory abnormalities, no AEs will be recorded; however, if an SAE or AE possibly related to the study procedure is screened, the corresponding AE/SAE should be recorded. No AE/SAE is required to be recorded after screening failure, i.e., "AE/SAE report is terminated when screening failure status is determined".

If a participant withdraws from the study and withdraws informed consent for future information collection, the AE/SAE reporting period is terminated at the time of withdrawal of consent.

8.3.14 Reporting Process for AEs and SAEs

Each participant must be carefully monitored for any adverse events. This information should be obtained in the form of non-leading questions (e.g., "How do you feel?"), as well as from signs and symptoms detected during each examination, observations by researchers, and spontaneous reports from participants.

All AEs (serious and nonserious) reported spontaneously by the participant and/or determined by answering open-label questions raised by the study personnel or by observation, physical examination, or other diagnostic procedures must be recorded. Whenever possible, signs and symptoms with common pathological features should be considered a composite event. Concomitant signs or symptoms (eg, abnormal laboratory values) should not be reported as additional adverse events. If the diagnosis is unknown, one or more symptoms may be

reported as separate adverse events. If the subsequently reported symptom is confirmed, the reported symptom term must be modified to "attributable" or "due to" the diagnosis.

All adverse events should be followed until resolution, stable disease, or until the investigator decides that follow-up is not required. After the safety reporting period, AEs determined to be unrelated to the investigational product will no longer be followed up.

For all SAEs occurring during the reporting period, whether initial or follow-up, regardless of causality, the investigator must report the SAE to the sponsor within 24 hours of awareness. SAEs must be followed until resolution, stable disease, or until the investigator decides that follow-up is not required. For study analysis, if the event is not resolved by the end of the study reporting period, it must be recorded as ongoing (not recovered/resolving). For regulatory safety monitoring purposes, a follow-up report should be sent as soon as more information becomes available.

The follow-up report should contain sufficient information required for a complete medical assessment and independent causality determination. All relevant information, such as concomitant medications and disease information, must be provided. For fatal cases, available summaries of necropsy or other death examinations must be submitted as soon as possible.

SAE initial and follow-up reports were submitted via email (contact details below).

All SAEs must be reported regardless of whether or not considered causally related to study drug. The sponsor may request the investigator to provide follow-up information on SAEs.

Contact Information	Sponsor Email: [contact]
---------------------	---------------------------------------

In the event of a suspected unexpected serious adverse reaction (SUSAR), the sponsor or its authorized representative will comply with the requirements of local regulatory authorities to ensure that the relevant regulatory authorities and all personnel involved in the study are notified as soon as possible. In accordance with local regulations and institutional policies, ethics committees (ECs)/institutional review boards (IRBs) and hospital facilities need to be notified of SUSARs or other required information.

8.3.15 Pregnancy Exposure

Participants are obligated to inform the investigator of any pregnancy that occurs during study treatment and up to 6 months after the last dose of study drug. Pregnancies occurring 6 months after the last dose of study drug or due to sperm donation/sperm preservation prior to study drug exposure are not reported.

Female participants who become pregnant during the clinical trial must immediately discontinue study drug and complete the Early Withdrawal Visit and the Safety Follow-up Visit. If the female partner of a male participant becomes pregnant during the study, the participant must immediately notify the investigator, and the male participant may continue the clinical study. Male participants must commit to use an acceptable method of contraception (to avoid or prevent fetal exposure to study drug) for the duration of the study until 6 months after the last dose of study drug. The investigator must notify the sponsor within 1 working day of becoming aware of the pregnancy of the participant (or his/her partner).

The participant or his/her spouse must be followed up until the end of pregnancy and the infant must be followed up to 1 month of birth, if informed consent is available. A separate

informed consent form (ICF) must be provided to explain these follow-up behaviors. Infant deaths after 1 month of life should also be reported as SAEs if assessed by the investigator as possibly related to study drug exposure. Pregnancy per se does not constitute an AE. Any adverse pregnancy outcome, such as stillbirth, spontaneous abortion, fetal malformation, is considered an SAE and needs to be reported as required for an SAE. The SAE Report Form and Pregnancy Report Form need to be completed separately for the same time limit as the SAE.

8.3.16 Death

All deaths occurring during the adverse event reporting period, whether related to study treatment or not, must be immediately reported to the sponsor as SAEs.

Deaths considered related to this study drug outside of the safety reporting period are required to be reported as SAEs.

8.4 Overdose

Any ABSK061 above the indicated dose will be considered an overdose. There is no specific antidote for ABSK061 and in the event of an overdose, participants should receive appropriate supportive care and record any AEs.

9 Statistical Methods

9.1 Sample Size Estimation

The objective of this study was to evaluate the PK profile of ABSK061 capsules in single or multiple oral doses, to assess the effect of soft food on the pharmacokinetics of ABSK061, and to explore the dose-exposure proportionality of ABSK061 microt. The sample size was estimated based on actual considerations and feasibility, and no hypothesis testing was performed.

The study was planned to enroll 18 participants in Part I and to be randomized in A 1: 1: 1 ratio to three different study sequences, A, B, and C.

Part II plans to enroll 12 participants and preset 2 study sequences (sequences D and E, 6/sequence).

Part III planned to enroll 12 participants and were randomized in a 1: 1: 1 ratio to three different study sequences: F, G, and H. Based on the data from the Phase 1 trial in patients with solid tumors of ABSK061-101, the weighted mean of the geometric coefficient of variation (CVw%) of each dose group was obtained for AUC0-∞, AUClast and Cmax. Considering that this was the inter-patient coefficient of variation, the intra-individual coefficient of variation (CVw%) in healthy participants in this study was estimated as 70% of the above-mentioned weighted mean, I.e. 27.272%, 27.384%, 21.966%. Although the sample size for this trial is not based on statistical testing, as a reference, it is assumed that there is no difference between the drug taken with water and with soft food. The two-sided 90% confidence intervals for the estimated precision (90% confidence interval half-width) and the Ratio of the Geometric Means Ratio (GMR) of the log-transformed PK parameters (taken with soft food-water) at different sample sizes are presented below.

Table of Estimated Accuracy of Primary PK Parameters at Different Sample Sizes (GMR =

1)

Part III							
Three-	AUC0-∞		AUClast		Cmax		
sequence,							
three-period	AU	€0-∞	AU	AUCIASI		Ciliax	
crossover							
design							
Evaluable Participants	Accuracy	GMR	Accuracy	GMR	Accuracy	GMR	
		90%		90%		90%	
		confidence		confidence		confidence	
		interval		interval		interval	
9		0.801,		0.800,		0.835,	
	0.222	1.249	0.223	1.250	0.180	1.198	
12		0.828,		0.828,		0.858,	
	0.189	1.208	0.189	1.208	0.153	1.165	
15		0.846,		0.846,		0.874,	
	0.167	1.182	0.167	1.182	0.135	1.145	

9.2 Dataset

The Screening Analysis Set includes all participants who signed informed consent. For participant disposition summaries and listings only.

The PK Concentration Analysis Set (PCS) includes all participants who have received at least one dose of ABSK061 in capsules and are able to provide at least one evaluable postdose PK blood sample. It will be the primary analysis set for all PK concentration data analyses.

The PK Parameters Analysis Set (PPS) includes all participants who are included in the PK concentration Analysis Set and have at least one PK parameter available for Analysis. It will be the primary analysis set for data analysis of all PK parameters.

The Safety Analysis Set (SST) includes all participants who received at least one dose of ABSK061 in capsules. Summary statistics and/or listings will be performed by treatment group actually received by the participant, primarily for safety analysis.

9.3 Statistical Analysis Methods

The statistical analysis of this study will be the responsibility of Shanghai Hezhui Biopharmaceutical Technology Co., Ltd. or its designee. Where applicable, data will be listed and summarized in accordance with Shanghai Hezhui Biopharmaceutical Technology Co., Ltd. or designee reporting criteria. Full details will be documented in the Statistical Analysis Plan (SAP).

9.3.1 General Methods

Descriptive statistics (mean, standard deviation, median, minimum, maximum) will be performed for continuous variables. Frequency distributions and percentages will be summarized for discrete variables. All available data will be included in the data listings.

Specific analyses of all endpoints will be detailed in the Statistical Analysis Plan (SAP).

9.3.2 Participant Disposition

Descriptive statistical analyses will be performed on the number of participants enrolled, received with study drug, reason for discontinuation by study sequence and overall, and the date and reason for discontinuation will be presented at the individual participant level.

9.3.3 Demographic and Baseline Characteristics

Demographic and other baseline data will be summarized descriptively by study sequence and overall based on the Safety Analysis Set.

9.3.4 Administration (study treatment, concomitant therapy, compliance)

All information related to drug management will be listed. Concomitant medications and important non-drug therapies prior to and after administration of study drug ABSK061 will be listed using the Safety Analysis Set.

9.3.5 PK Data Analysis

ABSK061 pharmacokinetic parameters will be calculated and analyzed by a standard noncompartmental model. The PK profile of single or multiple oral doses of ABSK061 microt was assessed based on the primary pharmacokinetic parameters obtained.

Results of PK parameters and summary data will be provided for each participant. Descriptive statistics (arithmetic mean, standard deviation, coefficient of variation, median, minimum, maximum, geometric mean, and geometric coefficient of variation) were calculated for all PK parameters of oral ABSK061 in each treatment group except for tmax, which will be summarized as median, minimum, and maximum. Data listings for all PK parameters will be provided.

Part III assessed the effect of coadministration with soft food on the PK profile of ABSK061. The main PK parameters (Cmax, AUC0- ∞ , AUClast) were log-transformed and statistically analyzed using a linear mixed-effects model. The dosing sequence and period in the model served as fixed effects and participants (in sequence) served as random effects. The magnitude of the difference between the Least Squares Means (and their 90% confidence intervals and the Ratio of the Geometric Least Squares Means (RGLSM, taken with soft food/water) and their 90% confidence intervals were estimated by logarithmic transformation, and the intra-individual coefficient of variation was calculated for each parameter.

In addition, the dose-exposure proportionality of ABSK061 microchips was explored by graphical presentation of different doses by primary PK parameters (Cmax, AUC0- ∞ , AUClast) and/or dose-normalized primary PK parameters for each treatment group. If applicable, the dose-exposure proportionality will be further explored through the Power model by natural log-transformation of the primary PK parameters.

The detailed analysis plan will be further described in the Statistical Analysis Plan (SAP).

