Part III is a three-period, three-sequence crossover study with the primary objective to evaluate the effect of co-administration of soft food on the PK of ABSK061. Part III plans to include 12 healthy participants randomized 1: 1: 1 to Sequence F, Sequence G, or Sequence H to receive a single oral dose of ABSK061 in triplicate doses of Treatment 1, Treatment 2, Treatment 3. Treatment 1 was 5 mg ABSK061 microchip taken with 180 mL of water, Treatment 2 was 5 mg ABSK061 microchip taken with a spoon of yogurt (approximately 15 mL), and Treatment 3 was administered with 5 mg ABSK061 microchip with a spoon of applesauce (approximately 15 mL). Participants in Sequence F will receive Treatment 1, Treatment 2, and Treatment 3 under fasting conditions in the morning on Cycle 1 Day 1 (D1), Cycle 2 Day 1 (D4), and Cycle 3 Day 1 (D7), respectively; participants in Sequence G will receive Treatment 2, Treatment 3, and Treatment 1 in the morning on D1, D4, and D7, respectively; participants in Sequence H will receive Treatment 3, Treatment 1, and Treatment 2 fasted in the morning on D1, D4, and D7, respectively. All participants were required to drink 180 mL of water immediately after swallowing the investigational drug. The washout period for each period was 3 days. The study design is shown in Table 3 Part III Study Design.

Table 3 Part III Study Design

	Cycle 1	Cycle 2	Cycle 3
Sequence F	Treatment 1	Treatment 2	Treatment 3
Sequence G	Treatment 2	Treatment 3	Treatment 1
Sequence H	Treatment 3	Treatment 1	Treatment 2

Note: Treatment 1: 5 mg ABSK061 micro-tablets were administered with 180 mL of water; treatment 2: 5 mg ABSK061 microchip + 1 tablespoon yogurt; treatment 3: 5 mg ABSK061 microchips + 1 tablespoon of applesauce. The washout period of each cycle was 3 days.

Investigati onal Product

ABSK061 capsules were manufactured and provided by the sponsor in two strengths: 0.2 mg/capsule, containing 4 0.05 mg tablets; 5 mg/capsule containing 10 0.5 mg tablets.

Mode of

The 1 mg dose corresponds to 5 capsules of the 0.2 mg strength, the 5 mg dose corresponds to 1 capsule of the 5 mg strength, the 10 mg dose

administra tion

corresponds to 2 capsules of the 5 mg strength, the 20 mg dose corresponds to 4 capsules of the 5 mg strength, and the 35 mg dose corresponds to 7 capsules of the 5 mg strength. The ABSK061 cap was opened prior to dosing and the microt was poured out and swallowed. See Section 7.6 Investigational Product Administration for details.

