Pharmacokinetic parameters of ABSK061 in capsules will be calculated and analyzed by a standard noncompartmental model. Results of PK parameters and summary data will be provided for each participant. Descriptive statistics (arithmetic mean, standard deviation, coefficient of variation, median, minimum, maximum, geometric mean, and geometric coefficient of variation) were calculated for all PK parameters except tmax, which will summarize the median, minimum, and maximum. Data listings for all PK parameters will be provided.

The PK profile of single or multiple oral doses of ABSK061 microt was assessed based on the main PK parameters obtained, the effect of oral administration with soft food on the pharmacokinetics of ABSK061, and the dose-exposure proportionality of ABSK061 microt was explored. Specific PK parameters include, but are not limited to, total drug exposure (AUC0- ∞ , AUClast), maximum concentration (Cmax), time to maximum concentration (tmax), elimination half-life (t1/2), apparent clearance (CL/F) and apparent volume of distribution (Vz/F), accumulation ratio (AR).

Part III evaluated the effect of co-administration of soft food on the PK characteristics of ABSK061, and natural log-transformation was performed on

the main PK parameters (AUC0- ∞ , AUClast, Cmax), and the Geometric Least Squares mean Ratio (Ratio in Geometric Least Squares Means, RGLSM, administered with soft food/water) was obtained by linear mixed model for statistical analysis and antilogarithmic transformation, and intra-individual coefficient of variation was calculated for each parameter.

The dose-exposure proportionality of ABSK061 administered as capsules in fasted water will also be explored by graphical presentation of primary PK parameters (AUC0- ∞ , AUClast, Cmax) and/or dose-normalized primary PK parameters. If applicable, the dose-exposure proportionality will be further explored through the Power model by natural log-transformation of the primary PK parameters.

The safety analysis set will be used for safety analysis. Safety will be assessed based on AE reporting, clinical laboratory data, vital signs, and electrocardiograms. Missing safety data will not generally be imputed unless otherwise specified.

End of Stu dy Criteria

A participant is considered to have completed the study if he/she has completed all visits to the study, including the last visit or last trial procedure shown in the flowchart.

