2.1 Primary Objective

- Part I: to evaluate the pharmacokinetic (PK) characteristics and safety of a single oral dose of ABSK061 microchip in healthy adult participants;
- Part II: to evaluate the safety, tolerability and PK profile of multiple oral doses of ABSK061 microchips in healthy adult participants;
- Part III: to evaluate the effect of ABSK061 microt 5 mg administered with soft food on the PK profile of ABSK061.

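### The Part III mixed model lists no treatment term, so the planned soft-food/water ratio and its 90% CI cannot be obtained from the model as stated

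*Protocol*

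**What the plan says.** The Part III objective in section 2.1 reads "Part III: to evaluate the effect of ABSK061 microt 5 mg administered with soft food on the PK profile of ABSK061". The synopsis states that "Part III is a three-period, three-sequence crossover study", with treatment orders F = 1-2-3, G = 2-3-1 and H = 3-1-2 (for example, "participants in Sequence G will receive Treatment 2, Treatment 3, and Treatment 1"). Treatment 1 is water, 2 is yogurt and 3 is applesauce, and 12 participants are allocated four to a sequence.

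Section 9.3.5 log-transforms Cmax, AUC0-∞ and AUClast, fits a linear mixed-effects model and names its terms: "The dosing sequence and period in the model served as fixed effects and participants (in sequence) served as random effects". It goes on: "the Ratio of the Geometric Least Squares Means (RGLSM, taken with soft food/water) and their 90% confidence intervals were estimated by logarithmic transformation". An intra-individual CV is also to be reported for each parameter.

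The only other description of this analysis, in the statistical methods part of the synopsis, says that the ratio "was obtained by linear mixed model for statistical analysis and antilogarithmic transformation". It lists no terms, so it does not supply the missing one.

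**The concern.** The quantity wanted is a contrast between treatments, and the model named to deliver it contains no treatment effect. Neither listed fixed effect can stand in for it. Every participant receives all three treatments, so sequence is not treatment. Participants are nested in sequence in the same sentence, which makes sense for F, G and H but not for water, yogurt and applesauce.

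Two planned outputs are affected. The food/water ratio and its interval are not estimable from the model, and the intra-individual CV absorbs any real food effect. If the term is added only at the analysis stage, the central model of Part III will differ from the one in the protocol, and the change could look data-driven.

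**Working it through.** **Inputs.** n = 12, four per sequence, three periods, hence 36 observations (synopsis; section 9.1). Intra-individual CVs of 27.272% (AUC0-∞), 27.384% (AUClast) and 21.966% (Cmax), two-sided 90% intervals and GMR = 1 (section 9.1).

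**1. Reproduce the protocol's own figures** (section 9.1, "Table of Estimated Accuracy of Primary PK Parameters at Different Sample Sizes").

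Half-width = t(0.95, df) × √ln(1 + CV²) × √(2/n); interval = exp(± half-width).

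For AUC0-∞, √ln(1 + 0.27272²) = 0.2678. At n = 12, √(2/12) = 0.4082.

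| AUC0-∞ | Stated | df = 2n-4 | df = 2n-2 |
|---|---|---|---|
| n = 9 | 0.222 (0.801, 1.249) | 0.2224 (0.801, 1.249) | 0.2204 (0.802, 1.247) |
| n = 12 | 0.189 (0.828, 1.208) | 0.1886 (0.828, 1.208) | 0.1878 (0.829, 1.207) |
| n = 15 | 0.167 (0.846, 1.182) | 0.1668 (0.846, 1.182) | 0.1664 (0.847, 1.181) |

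Over all three parameters, df = 2n-4 matches 9 of 9 half-widths and 18 of 18 interval limits to three decimals. With df = 2n-2 only 3 of 9 and 4 of 18 match.

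**2. Which model leaves which df.** With 3n observations, participants (sequence included) take n and periods take 2.

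- As written: 3n - n - 2 = 2n-2, which is 22 at n = 12.
- With a 2-df treatment effect: 3n - n - 2 - 2 = 2n-4, which is 20 at n = 12.

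The table in 9.1 therefore fits a model with treatment and does not fit the model in 9.3.5.

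**3. Estimability.** The fixed-effect design matrix has rank 5 as written (1 + 2 + 2) and rank 7 with treatment. The two missing dimensions are the two treatment contrasts.

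The same follows by hand for complete, balanced data. Let ȳ be the overall mean. The fixed-effect fit in sequence s and period p is ȳ(s) + ȳ(p) - ȳ. Each treatment occupies three sequence-by-period cells that cover every sequence once and every period once. Averaging the fit over those cells gives ȳ + ȳ - ȳ = ȳ for water, yogurt and applesauce alike. Any food/water ratio formed from these fitted means is exp(0) = 1.00. In 2,000 simulated trials with assumed true ratios of 1.5 (yogurt) and 0.7 (applesauce), the model as written gave 1.00 and 1.00; with treatment added it gave 1.50 and 0.70.

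**4. Effect on the intra-individual CV.** Without treatment, the expected residual variance is σ² + n × Σ(τ - τ̄)² / (2n-2), where τ are the log-scale treatment effects. For AUC0-∞, σ² = ln(1 + 0.27272²) = 0.0717. At n = 12 the multiplier is 12/22. CV = √(exp(variance) - 1).

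| Assumed true yogurt/water, applesauce/water | Σ(τ - τ̄)² | Added variance | CV reported |
|---|---|---|---|
| 1.00, 1.00 | 0 | 0 | 27.3% |
| 0.90, 0.90 | 0.0074 | 0.0040 | 28.1% |
| 0.80, 0.80 | 0.0332 | 0.0181 | 30.7% |
| 1.50, 0.70 | 0.2908 | 0.1586 | 51% |

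With treatment in the model the expected CV is 27.3% in every row. The ratios are illustrations; the protocol gives none except GMR = 1.

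**The case against.** The strongest reply is that the intended analysis is plain. A ratio labelled "RGLSM, taken with soft food/water" presupposes treatment means, the table in 9.1 fits a model with treatment, and the English of this paragraph is damaged: it has an unclosed bracket, and a logarithmic transformation where the synopsis has an antilogarithmic one. A term may have been lost in translation. Section 9.3.5 also defers detail to the SAP, which is not at hand. A competent analyst would find the treatment means undefined and add the term, so a falsely reported ratio of 1.00 is unlikely. No formal hypothesis test or decision rule hangs on the result.

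Much of this stands. The realistic harm is a late departure from the stated model rather than a wrong published ratio. The ratio of 1.00 is an algebraic identity for complete data and adds nothing to the rank argument. The CV inflation depends on an assumed food effect and vanishes when there is none. The 2n-4 match is consistent with a treatment effect but cannot by itself identify which 2-df within-participant term was meant. The section 2.1 objective is the effect on the PK profile; the ratio with its interval is how 9.3.5 analyses it.

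None of it makes the sentence right. The protocol does not leave the terms to the SAP; it states them, and states them so that the required contrast is missing. A SAP that repeats the sentence carries the fault forward, and one that adds treatment departs from the protocol. Descriptive geometric means by treatment group do not supply the model-based ratio and 90% CI that the paragraph requires.

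**Conclusion.** The point holds and needs correction before analysis. The Part III model as written cannot yield the soft-food/water ratio or its 90% CI. This follows from the design and the listed terms alone and needs no assumption about the data. The protocol's sections disagree: 9.1 fits 2n-4 degrees of freedom (20 at n = 12), whereas the model in 9.3.5 leaves 2n-2 (22). The secondary effect, an inflated intra-individual CV, depends on the true food effect: none at a ratio of 1, about 30.7% instead of 27.3% if both ratios are 0.80, and more if the two foods act in opposite directions.

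**What to change.** In section 9.3.5, restate the model with treatment (water, yogurt, applesauce), sequence and period as fixed effects and participant within sequence as a random effect. State that the yogurt/water and applesauce/water ratios are the treatment least-squares-mean contrasts on the log scale, exponentiated together with their 90% confidence limits, and that the intra-individual CV comes from the residual variance of this model. Use the same wording in the SAP.

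The cost is one sentence in each document, made before the data are analysed. Design, sample size, data collection and the precision table in 9.1 stay as they are; the table already agrees with the corrected model.
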